#### A3. PROPOSAL TITLE

Effectiveness of Nursing Educational Intervention on Vascular Access Self-Care in Hemodialysis

#### A4. SUBJECT AREA

Transition process to self-care with vascular access

#### A5. STUDY DESIGN

Prospective, quantitative, cross-sectional study, employing a quasi-experimental methodology that involves an initial diagnostic assessment, a subsequent educational intervention to promote adherence to self-care, and an evaluation of outcomes after this intervention.

“Quasi-experimental studies fall within a positivist methodology, as they have a quantitative nature. The way in which the researcher controls the groups exposed to the study and the

manner in which interventions are carried out lead to expected outcomes, that is, an induction of results" (Soares, 2021).

## B. BRIEF STUDY PROTOCOL SUMMARY

### B1. SUMMARY

Background: Chronic Kidney Disease (CKD) is a condition that causes a slow, progressive, and irreversible loss of kidney function (Martins & Moura, 2023). The global incidence of this disease has been increasing and is currently a matter of great importance. At an advanced stage, renal replacement therapy is required, and Hemodialysis (HD) is the treatment of choice.

The therapeutic regimen of HD patients includes blood pressure control, glycemic control, anemia management, fluid and dietary restrictions, pharmacological regimen, vascular access care, and renal replacement techniques (Ordem dos Enfermeiros, 2016).

According to Barros (2020), "patients with CKD have educational needs for effective self-management of the therapeutic regimen." Self-management is defined by Shen et al. (2019) as the ability of an individual to manage symptoms, treatment, physical and psychosocial consequences, and lifestyle changes inherent to living with a chronic condition. In chronic disease self-management, "health promotion through encouragement of self-care" is considered fundamental, leading "nursing to provide interactive care, constructed jointly and empowering" (Rocha et al., 2020). Health literacy and the acquisition of knowledge for self-management of the health–disease transition process in CKD patients are essential for adherence to the therapeutic regimen and self-care.

Within active participation in their treatment, care of the Vascular Access (VA) is included. For HD treatment, there are three main types of VA: arteriovenous fistulas (AVF), arteriovenous grafts (AVG), and central venous catheters (CVC). According to Pinto et al. (2022), "the creation and maintenance of a functional vascular access is crucial for effective hemodialysis therapy" and "the importance of vascular access in patient care (...) is recognized by all health professionals and is a determining factor in the success of care and treatment effectiveness" (Ordem dos Enfermeiros, 2016). Arasu et al. (2022) add that in selecting the type of access, a "pragmatic and patient-centered approach" is required. The AVF is the preferred access for HD, as it has the longest lifespan and lowest complication rates (Arasu et al., 2022) and is also associated with lower morbidity and mortality in CKD patients (Murea et al., 2019).

The nurse is primarily responsible for VA assessment and physical examination prior to treatment and plays a key role in identifying dysfunction. Thus, “the nurse should empower patients and guide them to recognize the necessary care for the vascular access, in order to facilitate adherence to the new routines imposed by treatment through teaching self-care” (Rocha et al., 2020).

Regarding VA care, Rocha et al. (2020) note that such care is not limited to treatment sessions but is also constant at home, where the patient “takes an even greater role, demonstrating commitment to the treatment through self-care.” Therefore, they must perform actions to ensure proper development and maintenance of the AVF. Martins and Moura (2023) add that self-care for VA “translates into spontaneous and purposeful behaviours by the patient aimed at promoting health and well-being and ensuring proper vascular access functioning.”

Given the complexity of these interventions and the considerable care needs, it is essential to develop differentiated care models that incorporate new nursing roles, in addition to those specific to HD treatment. In this context, the nurse acts as a promoter of patient self-management, actively contributing to improving the quality of life of individuals with chronic conditions (Ma et al., 2022; Mansoor & Khuwaja, 2020).

In nursing practice, it becomes necessary to provide care with a positive impact on clinical and health/quality-of-life outcomes; to establish personalized care plans based on individual needs and vulnerabilities; to provide patients and their caregivers with sufficient knowledge about their situation—health literacy; and to empower patients to be as autonomous as possible, including promoting self-care with their VA.

To achieve this, “the nurse should use a systematic approach to assess and identify the nursing care needs of the patient. In particular, a careful assessment of their knowledge about the disease and treatment process (...) aiming at well-being and meeting their needs. The nurse should also identify diagnoses, define, and implement interventions to achieve nursing-sensitive outcomes” (Ordem dos Enfermeiros, 2016).

Considering this, it is essential to evaluate the impact of nursing interventions on promoting patient self-care, with one key area of study being the impact of nursing educational intervention on self-care adherence. To plan and tailor care appropriately, it is important to understand the “starting point,” i.e., to assess the self-care profile regarding VA in a group of HD patients, to define, implement, and evaluate the impact of an intervention plan.

Thus, the objectives of the present study are:

1. To assess the self-care profile regarding VA in a population of CKD outpatients in HD units;
2. To evaluate the impact of nursing educational interventions on the transition process to self-care with VA in this population.

To address these objectives, the following research question was formulated: What is the impact of nursing educational intervention on the transition process to self-care with vascular access in outpatients undergoing hemodialysis?

## METHODS

Study type: Prospective, cross-sectional, quantitative study aimed at evaluating the effectiveness of nursing educational intervention on VA self-care. This study follows a quasi-experimental methodology, involving an initial diagnostic assessment, a set of health education sessions, and a subsequent evaluation of the results of this educational intervention.

Population and sample: The population will consist of individuals with CKD undergoing outpatient HD at two HD units in the central region of Portugal. The sample will be non-probabilistic and selected by convenience, including CKD patients in HD whose VA in use is an AVF, from the two aforementioned HD units.

Inclusion criteria:

- Individuals with CKD in HD;
- Independent in self-care;
- With VA – AVF.

Exclusion criteria:

- VA via CVC or AVG;
- Cognitive impairment (assessed using the Mini Mental State Examination – MMSE – developed by Folstein et al., 1975);
- Lack of fluency in Portuguese.

Data collection instrument: The study will use a data collection instrument consisting of three parts: sociodemographic characterization, clinical characterization of participants, and assessment of AVF self-care behaviours.

The first two parts will include:

- Sociodemographic variables: age (years), sex (male/female), household composition (number of members), education level (illiterate, primary, secondary,

higher education), and employment status (employed, unemployed, homemaker). Categorical variables will be assessed through closed-ended questions, and age will be a continuous variable (years).

- Clinical variables: CKD etiology (diabetes, hypertension, polycystic kidney disease, glomerulonephritis, hypoplasia/dysplasia, unknown, or other causes), HD duration (years), duration of HD with AVF, AVF location/type (cubitocubital, radiocephalic, humerobasilic, humerocephalic, humerohumeral), and previous VA complications (thrombosis and infection episodes). Clinical data will be obtained from patient medical records.

Self-care behaviours will be assessed using the **Scale for Assessment of Self-Care Behaviours with AVF in HD** developed by Sousa et al. (2015), consisting of 16 items, structured into two dimensions:

1. *Prevention of complications* – 10 items assessing behaviours related to preventing AV thrombosis and infection;
2. *Management of signs and symptoms* – 6 items assessing self-care behaviours related to detecting VA complications.

In its original study, this scale showed good reliability (Cronbach's alpha: global 0.80; prevention subscale 0.72; management subscale 0.80).

A pilot test will be conducted with 4 patients to assess applicability, clarity, and completion time.

Data collection procedure: Participants will be recruited by designated study liaisons from each HD unit, in close collaboration with the principal investigator, according to inclusion/exclusion criteria. Eligible patients will be invited to participate and given full study information. Those who agree will provide written informed consent.

First phase: sociodemographic and clinical data collection and administration of the AVF self-care scale. Data will be collected by the principal investigator, in person, with manual completion of the scale. Duration: ~1 month.

Intervention phase: Based on the first assessment results, patients with suboptimal behaviours will receive a tailored nursing educational intervention—a series of health education sessions integrated into HD sessions—each lasting approximately 30 minutes.

Second phase: Three months later, the scale will be re-administered to all initial participants, regardless of the need for intervention. Data collection will again be by the principal investigator, in person, with manual completion. Duration: ~1 month.

Each participant will be assigned an alphanumeric code for pairing pre- and post-intervention data. The code–name key will be accessible only to the principal investigator.

Nursing educational intervention: A set of individual health education sessions, delivered using expository methods and an informational leaflet, focusing on:

- Prevention of thrombosis and infection (recognition of complications during and between HD sessions, hemostasis care, limb protection from trauma, avoidance of non-HD punctures);
- Correct assessment of signs/symptoms suggestive of AVF complications (AVF functionality assessment via thrill palpation, detection of thrombosis by absence of thrill, changes in colour/sensation of the limb, limb pain).

The sessions will be conducted by the principal investigator.

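### Does calling the sample a convenience sample leave room for selective invitation, so that the recruitment rule for the baseline self-care profile needs rewriting?

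*Combined protocol and SAP*

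**What the plan says.** Under METHODS, the population and sample paragraph sets the source population: "The population will consist of individuals with CKD undergoing outpatient HD at two HD units in the central region of Portugal". The sample is then called non-probabilistic and "selected by convenience, including CKD patients in HD whose VA in use is an AVF, from the two aforementioned HD units". One of the exclusions is "Cognitive impairment (assessed using the Mini Mental State Examination".

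The data collection procedure, also under METHODS, says how people enter the study: "Participants will be recruited by designated study liaisons from each HD unit, in close collaboration with the principal investigator, according to inclusion/exclusion criteria". It continues "Eligible patients will be invited to participate and given full study information", and then "Those who agree will provide written informed consent". For the first phase, "Data will be collected by the principal investigator, in person, with manual completion of the scale. Duration: ~1 month". The second assessment is explicitly for everyone assessed at the first.

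The first objective in section B1 is "To assess the self-care profile regarding VA in a population of CKD outpatients in HD units". DATA ANALYSIS plans descriptive statistics for participants, percentages of responses on the scale and an inferential pre-post comparison. The available text plans no count of patients screened, eligible, invited or declining. Some pages were not available for this review, so that absence is judged on the visible text only.

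**The concern.** The patients of two dialysis units can be listed, so a convenience sample is not forced on the investigator. Read strictly, the phrase would let a liaison approach the patients who are easiest to reach, or the most cooperative. Those patients may look after their fistula better or worse than the rest.

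For a descriptive objective this matters directly. Any such difference goes into the reported percentages, and a larger sample chosen in the same way would not remove it. Without counts of eligible, invited and declining patients, a reader could not judge coverage. The second objective is less exposed: it compares patients with themselves, so selection bears mainly on how far the result generalises.

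**Working it through.** **Is there a figure to reproduce?** No. The documents give no sample size, roster size, invitation share or expected acceptance. The check is a reading of the text, followed by an illustration on assumed inputs.

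**Reading the text**

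1. The population and sample paragraph names a sample type (non-probability, convenience) and a frame (fistula patients at two units). It describes no step that picks some eligible patients over others.
2. The data collection procedure gives the operating rule: recruitment follows the inclusion and exclusion criteria, eligible patients are invited, and those who agree consent. Meeting the criteria leads to an invitation.
3. The two are compatible. A sample from two accessible units is commonly called a convenience sample even when every eligible patient there is approached.
4. One ambiguity remains. The reassessment sentence covers everyone explicitly, while the invitation sentence has no such word.

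**What a stricter rule could gain (all inputs assumed)**

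Let i be the share of eligible patients invited, a the share accepting, r = i × a the share assessed, and p the observed proportion with a given behaviour. With nothing assumed about unassessed patients, the proportion among all eligible patients lies in [r·p, r·p + 1 − r], a width of 1 − r. If assessed and unassessed patients differ by d, the bias is (1 − r) × d. Take p = 0.60, a = 0.80 and d = 10 points.

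| i | r = i × 0.80 | Lower = r × 0.60 | Upper = lower + 1 − r | Width | Bias = (1 − r) × 10 |
|---|---|---|---|---|---|
| 0.70 | 0.56 | 0.336 | 0.776 | 0.44 | 4.4 points |
| 0.90 | 0.72 | 0.432 | 0.712 | 0.28 | 2.8 points |
| 1.00 | 0.80 | 0.480 | 0.680 | 0.20 | 2.0 points |

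The width removed by inviting everyone is (1 − 0.80i) − 0.20 = 0.80 × (1 − i):

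- i = 0.70: 0.80 × 0.30 = 0.24
- i = 0.90: 0.80 × 0.10 = 0.08
- i = 1.00: 0

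The remaining 0.20 comes from refusals, which no invitation rule removes.

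**Limits of the illustration.** The widths are worst-case bounds, not estimates of bias. The bias column holds d fixed across rows, and is zero if d = 0. The bounds hold p at 0.60 across rows, although p would move if newly invited patients differed, which is the very worry. The whole gain comes from the assumed shortfall in i, for which the documents give no evidence.

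**The case for a change.** The best case for a change is as follows. The two units already define the population, and the sample is selected from them, so on the grammar *convenience* seems to apply to patients rather than units. The author wrote an explicit *all* for reassessment and not for invitation. ETHICAL PROCEDURES has every file destroyed when the study ends, so a count not made in time may be lost. The remedy is a few words and a tally, and TIMELINE already has a participant identification step where it could start.

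Part of this stands. The wording does not strictly exclude selective invitation, and noting decliners as recruitment proceeds is sensible. But the grammatical argument sets a label against the only sentence that says what the liaisons do, and that sentence has no selection step. If the investigator means to invite everyone eligible, the new wording alters nothing in conduct. Patient-flow counts are a reporting matter that the investigator and liaisons can handle during recruitment without altering the design. A fallback such as approaching patients in random order would answer a shortage of capacity that nothing in the documents shows.

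The stakes are also modest and largely disclosed. Non-probability sampling from two units is stated openly. Section B1 presents the profile as a baseline from which to tailor the intervention, and DATA ANALYSIS plans simple percentages with no stated inference to a wider population.

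**Conclusion.** No change to the plan follows. The sample label and the invitation rule do not conflict. What is left is one missing word and an unplanned participant count, both of which a careful investigator would ordinarily supply in conduct and reporting.

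The size of any bias is unknown. The illustration gives 4.4 points against 2.0, but only with an assumed 70% invitation share, 80% acceptance and a 10-point difference. The gain from a rewritten rule falls to zero if all eligible patients are invited. The conclusion rests on reading the recruitment sentences in their ordinary sense, that a patient who meets the criteria is invited. Evidence that liaisons approached only some eligible patients would reopen the question for the first objective; for the second it would still bear mainly on generalisability.

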## **DATA ANALYSIS**

Data analysis will be organized in two parts:

Part 1 – Sociodemographic and clinical variables:

- Mean and median for quantitative variables (age);
- Absolute frequencies and percentages for categorical variables.

Part 2 – Scale results:

- Results presented as percentage of responses, as recommended by the scale's author.

Impact assessment:

Inferential statistics will be used to compare VA self-care behaviours between the two data collection moments (pre- and post-intervention).

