**TIMELINE:**

Activities	04/2024	05/2024	06/2024	07/2024	08/2024	09/2024	10/2024	11/2024	12/2024	01/2025	02/2025	03/2025	04/2025	05/2025
Literature Review														
Participant identification														
Data Collection (moment 1)														
Data analysis														
Intervention preparation														
Intervention														
Data Collection (moment 2)														
Data analysis														
Interpretative results analysis														
Final report and submission														

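### Only some patients are taught but all are re-measured, and the sole pre/post comparison cannot separate a teaching effect from change that would have happened anyway

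*Combined protocol and SAP*

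**What the plan says.** Under Methods, the study is "aimed at evaluating the effectiveness of nursing educational intervention on VA self-care", and the second objective in the Summary is to evaluate the impact of the teaching. The data collection procedure then sets three things:

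- Who is taught: "Based on the first assessment results, patients with suboptimal behaviours will receive a tailored nursing educational intervention". No score, item count or percentage defines suboptimal.
- Who is re-measured, at three months: "the scale will be re-administered to all initial participants, regardless of the need for intervention".
- How records are linked: "Each participant will be assigned an alphanumeric code for pairing pre- and post-intervention data". The data collection instrument has sociodemographic, clinical and scale parts. Taught status and number of sessions are not listed.

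Under Data Analysis, the impact assessment uses unnamed inferential statistics to "compare VA self-care behaviours between the two data collection moments (pre- and post-intervention"). No taught/untaught term and no baseline adjustment is mentioned. The protocol states no sample size, power or expected effect.

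**The concern.** The plan already collects before and after scores on any patients who are not taught, but the analysis makes no use of the distinction. Two things follow if the comparison is made over all participants. A real effect is diluted, because patients who received nothing are averaged in. And any change shared by everyone, such as familiarity with the scale or routine advice in the unit, is counted as if it were due to teaching.

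At stake is the main conclusion. A significant rise could be reported as effectiveness when teaching did nothing, and a useful effect in a minority could look small.

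**Working it through.** There is no sample size or power figure in the protocol to reproduce. What follows is illustration under assumptions: scores in baseline SD units, equal SD at both times, normal scores, pre/post correlation r = 0.6–0.8, share taught p = 30–70%, two-sided 5% level. The patients taught are those with the lowest baseline scores.

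**1. What the pooled change measures.** Mean change = p × D + drift, where D is the teaching effect.
- D = 0.5, p = 0.3, drift 0: 0.3 × 0.5 = 0.15 SD.
- D = 0, drift 0.15: 0.15 SD.

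The two cases have the same mean change. With p = 0.5 or 0.7, the 0.5 SD effect appears as 0.25 or 0.35 SD.

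**2. How often drift alone would be significant.** For a paired test on N patients, the SD of change is √(2(1 − r)): 0.894 at r = 0.6 and 0.632 at r = 0.8. The chance of significance is approximately Φ(drift × √N / SD of change − 1.96). With drift 0.15 and D = 0:

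| N | r = 0.6 | r = 0.8 |
|---|---|---|
| 60 | Φ(1.30 − 1.96) = 25% | Φ(1.84 − 1.96) = 45% |
| 100 | Φ(1.68 − 1.96) = 39% | Φ(2.37 − 1.96) = 66% |
| 150 | Φ(2.05 − 1.96) = 54% | Φ(2.90 − 1.96) = 83% |

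Simulation agrees: 24–46%, 36–66% and 51–83%.

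**3. Why the raw taught-minus-untaught difference in change is not the answer.** The taught are chosen for low scores, so they rise by regression to the mean, and the untaught fall. With c the cut-point for share p, and no effect or drift, the taught gain (1 − r)φ(c)/p and the untaught change by −(1 − r)φ(c)/(1 − p). At r = 0.7 and p = 0.5, that is 0.3 × 0.399/0.5 = 0.239 and −0.239, a spurious difference of about 0.48 SD. Across r = 0.6–0.8 and p = 0.3–0.7 it is 0.32–0.66 SD. Weighted by group size, the two shifts cancel, so the pooled change is not affected by this selection.

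**4. What baseline adjustment does.** Regress the second score on the baseline score and taught yes/no. With no effect and 0.15 SD drift, the taught coefficient was significant in 4–6% of simulated studies. With a uniform effect of 0.5 SD it averaged about 0.50. The regression needs the taught indicator; it does not need the cut-off value as an input.

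**5. Its precision.** SE = √[(1 − r²)V / (N p(1 − p))], with V = 1/(1 − φ(c)²/(p(1 − p))), which is 2.75 at p = 0.5 and 2.36 at p = 0.3 or 0.7. At N = 100:
- smallest: √(0.36 × 2.75/25) = 0.199
- largest: √(0.64 × 2.36/21) = 0.268

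Simulated power for 0.5 SD is about 43–68% at N = 100 and 29–48% at N = 60.

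**6. Where it fails.** Suppose the effect averages 0.5 SD among the taught but grows from zero at the cut-point with distance below it. The coefficient then reads 0.26, 0.00 and −0.16 at 30%, 50% and 70% taught. Separately, with a uniform 0.5 SD effect and a scale ceiling 0.5 SD above the baseline mean, it reads 0.48, 0.34 and 0.15.

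**The case against.** A one-group before/after comparison is a legitimate choice for a small quasi-experimental student project, and it remains valid as a description of change. That stands, and the comparison should be kept.

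Three stronger readings are tempting, and the documents do not support them.

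- A reader might infer that nobody will know who was taught. The protocol is only silent on this. The principal investigator scores the scale, gives every session and holds the code key, so could easily record it. The gap is that taught status is neither listed as a data item nor used in the analysis.
- A reader might infer that a strict total-score cut-off is essential and would recover the true effect. With taught status recorded, the regression runs without the cut-off value. Whether it recovers the effect depends on how teaching works across the score range (step 6). Because teaching is tailored, larger gains in worse scorers are plausible. Suboptimal behaviours may also mean item-level need, and a rigid total-score rule could withhold teaching from a patient with a good total and one unsafe habit.
- A reader might take the pooled paired test as the plan's own. The protocol names no test and does not say which patients enter it. Restricting the comparison to the taught would avoid dilution but not drift, and would add the regression to the mean in step 3.

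The 30–70% range for the share taught has no basis in the documents. If nearly everyone has some suboptimal item, there will be no usable comparison group.

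**Conclusion.** The concern holds. As written, the impact comparison measures change over time. Read over all participants, it shrinks a teaching effect in proportion to the share taught and cannot tell it from drift: 0.15 SD arises equally from a 0.5 SD effect in 30% of patients and from drift with no effect. Under that drift alone, false claims of benefit would occur in roughly a quarter to two thirds of studies of 60 to 100 patients.

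These sizes rest on assumed sample size, correlation, drift, effect and share taught. The structural point does not. A baseline-adjusted comparison on data already collected would bear more directly on the stated aim. It is supportive evidence and not definitive: it assumes a straight-line relation between the two scores, a roughly uniform effect and no strong ceiling.

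**What to change.** 1. Before the first assessment, write down the rule that makes a patient suboptimal, by total score or by item, as clinically appropriate. Enter taught yes/no and number of sessions in the database under the existing participant code.
2. Report pre/post change separately for taught and untaught patients, labelled as change over time. Do not interpret the raw difference between the two changes.
3. Add a secondary regression of the second score on baseline score and taught yes/no, with a 95% CI, stating which numeric score is used. Add a sensitivity analysis in which the effect may vary with baseline.
4. State in advance how few untaught patients would be too few. Below that, report change over time only and make no effectiveness claim.

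A strict total-score cut-off would strengthen the comparison but is optional, given the clinical drawback noted above.

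The cost is a written rule, two fields per patient and one regression with its sensitivity analysis, with no extra patients or visits. Precision will be limited, and the adjusted estimate may understate a real effect. The change does not remove bias from one person both teaching and scoring, or spill-over between patients in the same unit.
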